9.4. Analyses of Secondary Efficacy Endpoints

The analyses on secondary efficacy endpoints are discussed according to the analysis phase in the following two sections.

9.4.1. Secondary Efficacy Endpoints in the Placebo-controlled Phase

All analyses will be conducted using ITT population including data from the Placebo-controlled Phase (Week 0 to Week 16). Table 5 is the summary on how the secondary efficacy endpoints at Week 16 will be analyzed.

Table 5 Analysis on the Secondary Efficacy Endpoints at Week 16

Summary Measure of Endpoint	Primary Analysis	Supportive Analysis
Mean change from baseline in DLQI at Week 16	ANCOVA model adjusted by baseline DLQI score, treatment, stratification factor on data with MI	ANCOVA model adjusted by baseline DLQI score, treatment, stratification factor on data with LOCF
Mean percent change in Body Surface Area (BSA) affected by psoriasis at Week 16	ANCOVA model adjusted by BSA score, treatment, stratification factor on data with MI	ANCOVA model adjusted by BSA score, treatment, stratification factor on data with LOCF
Mean change from baseline in Pruritus Numeric Rating Scale (NRS) score at Week 16	ANCOVA model adjusted by baseline NRS score, treatment, stratification factor on data with MI	ANCOVA model adjusted by baseline NRS score, treatment, stratification factor on data with LOCF
Mean change from baseline in skin discomfort/pain Visual Analog Scale (VAS) at Week 16	ANCOVA model adjusted by baseline VAS score, treatment, stratification factor on data with MI	ANCOVA model adjusted by baseline VAS score, treatment, stratification factor on data with LOCF
Proportion of subjects who achieve Psoriasis Area Severity Index (PASI) < 3 at Week 16	CMH test adjusting for the stratification factor on data with MI	CMH test adjusting for the stratification factor on data with LOCF and data with NRI
Proportion of subjects who achieve Patient Benefit Index (PBI) global score of ≥ 1 at Week 16	CMH test adjusting for the stratification factor on data with MI	CMH test adjusting for the stratification factor on data with LOCF and data with NRI
Mean percent change from baseline in European Quality of	ANCOVA model adjusted by baseline EQ-5D score*, treatment,	ANCOVA model adjusted by baseline EQ-5D score*, treatment,

Apremilast

Statistical Analysis Plan. Protocol CC-10004-PSOR-020

Amgen INC.

Life 5-Dimension (EQ-5D) score* at Week 16	stratification factor on data collected on scheduled Week 16 visit	stratification factor on end of phase assessment
Mean change in Work Productivity and Activity Impairment Questionnaire: Psoriasis (WPAI: PSO) domain scores** at Week 16	ANCOVA model adjusted by baseline Psoriasis WPAI score**, treatment, stratification factor on data collected on scheduled Week 16 visit	ANCOVA model adjusted by baseline Psoriasis WPAI score**, treatment, stratification factor on end of phase assessment
*two variables will be evaluated individually: EQ-5D VAS and EQ-5D index value		
**four variables will be evaluated individually: percentage work missed, work impairment, overall work impairment, and activity impairment		

For each continuous-like efficacy assessments, the SAS procedure MI will be used to impute missing values for each scheduled visit in the Placebo-controlled Phase (Weeks 0 to 16). There are exceptions for the EQ-5D assessment and WPAI: PSO assessment, which are only assessed at Week 16/discontinuation visit in the Placebo-controlled Phase. For these two endpoints, no missing data imputation will be conducted and the analyses will be conducted on assessments collected at the scheduled Week 16 visit as well as on assessments collected at end of phase (section 5.5).

For MI, the missing data patterns will be checked by treatment and stratification factor at Baseline (Week 0), and Weeks 2 (if applicable), 4, and 16. If there are non-monotone missing patterns, two separate imputation procedures will be used to complete the imputation process. In case of convergence issue, same strategy as for the primary endpoint will be followed.

In the first step, the Markov Chain Monte Carlo (MCMC) method will be used to impute missing data by baseline value, treatment and stratification factor to create M=25 imputed data sets with monotone missing patterns. The minimum and the maximum values for imputation will set depending on the range of the corresponding score of interest. The seed will be set to 804529, the imputed values will be rounded to integers and a single chain will be used to produce imputations. This step will be skipped if the data missing pattern is monotone.

In the second step, the predictive mean matching method will be used to impute the remaining missing values for the 25 data sets with monotone missing patterns. The MONOTONE REGPMM statement will be used with seed 447159. The missing values at each visit will be imputed based on treatment, stratification factor, and the score of interest at baseline and previous visits. The number of closest observations to be used in the selection will be K=5 for DLQI, skin discomfort/pain VAS, BSA, as well as PASI and K=2 for PBI.

The binary endpoints at Week 16 will be analysed similarly as the primary endpoint. Missing data from the original continuous-like score will be handled by multiple imputation (MI) as the primary approach. The response variable will then be derived based on the continuous score. Statistical outputs from each of the imputed complete data sets will be combined in making statistical inferences. For the combined inference, the response rates for each treatment arm and differences

Apremilast**Statistical Analysis Plan. Protocol CC-10004-PSOR-020****Amgen INC.**

for treatment comparison were the averages from the 25 imputed data sets. The difference of the response rate (Apremilast 30 mg BID - placebo) and its 95% CI as well as the p-value will be produced using the Cochran-Mantel-Haenszel (CMH) test and adjusting for the stratification factor at randomization. SAS PROC FREQ with the COMMONRISKDIFF (TEST=MH) option will be used for the analysis. Same analyses will also be conducted for other scheduled assessment visits (e.g., at Week 2 and Week 4) during the Placebo-controlled Phase. In addition to the MI method, supportive analyses using CMH method for the binary endpoints will be performed on data with LOCF and data with NRI. Same analyses will be repeated for assessments scheduled at time points before Week16.

For continuous endpoints, missing data will be imputed by MI as the primary approach. Change (or percent change) from baseline in each score at Week 16 will be analyzed using the same analysis of covariance (ANCOVA) model to analyze the 25 complete datasets and the SAS procedure MIANALYZE will be used to combine the results for the statistical inferences. The ANCOVA model will use the change (or percent change) from baseline as the dependent variable and will include treatment group and stratification factor as independent variables as well as the baseline value as a covariate variable. Within-group least-squares (LS) mean changes from baseline at Week 16, the associated standard errors (SEs) and 2-sided 95% CIs, treatment differences in LS mean changes from baseline, and the associated 2-sided 95% CIs and p-values, will be derived from the ANCOVA model based on each of the 25 complete datasets. Same analyses will also be conducted for other scheduled assessment visits (i.e., at Week 2 and Week 4) during the Placebo-controlled Phase. In addition to the MI method, supportive analyses using ANCOVA model for the continuous endpoints will be performed on data with LOCF. The same analyses will be repeated for assessments scheduled at time points before Week16. Summary statistics will also be provided by treatment and time point based on Data as Observed (DAO) for each continuous variable.

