4.2. Inclusion Criteria

Subjects must satisfy the following criteria to be enrolled in the study:

1. Subject is \geq 18 years of age at the time of signing the informed consent form (ICF).
2. Subject must understand and voluntarily sign an ICF prior to any study-related assessments/procedures being conducted.
3. Subject is willing and able to adhere to the study visit schedule and other protocol requirements.
4. Subject has diagnosis of chronic plaque psoriasis for at least 6 months prior to baseline, that cannot be controlled by topical therapy.
5. Subject has a PASI score ranging from ≥ 3 to ≤ 10 at baseline.
6. Subject has a DLQI score > 10 at baseline.
7. Subject has presence of ≥ 1 clinical manifestations of plaque psoriasis, defined as at least one of the following:
 - a. Moderate to severe scalp psoriasis, defined as Scalp Physician Global Assessment (ScPGA) ≥ 3
 - b. Nail psoriasis, defined as onycholysis and onychodystrophy in at least 2 fingernails
 - c. Moderate to severe genital plaque psoriasis, defined as modified static Physicians Global Assessment of Genitalia (sPGA-G) ≥ 3
 - d. Moderate to severe palmoplantar psoriasis, defined as Palmoplantar Psoriasis Physicians Global Assessment (PPPGA) ≥ 3
 - e. Moderate to severe plaque psoriasis in visible locations (dorsal hand, face, neck, and hairline) with static Physicians Global Assessment (sPGA) ≥ 3
8. Subject must be in general good health (except for psoriasis) as judged by the Investigator, based on medical history, physical examination, and clinical laboratories. (NOTE: The definition of good health means a subject does not have uncontrolled significant co-morbid conditions.)
9. Subject must have failed to respond to, or be contraindicated to, or intolerant to other systemic therapy including, but not limited to, cyclosporine, methotrexate, acitretin, psoralen and ultraviolet-A-light (PUVA), fumaric acid esters or biologic therapies.
10. Subjects (**in Italy only**) must be non-responder to, contraindicated to, or intolerant to other systemic therapy (including cyclosporine, methotrexate, or PUVA) **AND** also be contraindicated to, or intolerant to biologics.

Approved

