9.6.2. Secondary and Exploratory Efficacy Endpoints

For continuous endpoints at Week 16, an analysis of covariance (ANCOVA) model with treatment and randomization strata as fixed effects and corresponding baseline value as a continuous covariate will be employed. Missing data will be addressed using multiple imputation. The adjusted means and standard errors will be reported for each of the treatment group using the ANCOVA model, as well as the estimated treatment effect (ie, difference in the adjusted treatment means, their standard errors, and 95% confidence intervals). In addition, descriptive statistics will be provided based upon the observed data which will not address missing data. Details regarding the methods of estimation to be performed at Weeks 32 and 52 will be provided in the statistical analysis plan (SAP).

[figure not shown]
For discrete endpoints, the CMH estimation method stratified by the randomization strata for assessing the difference in proportion between the treatment groups will be conducted. The weights in the CMH estimation method will be same as those used in the primary endpoint analysis. The adjusted difference in the proportions between the treatment groups, their standard errors, and corresponding 95% confidence intervals will be reported. Missing data will be addressed through multiple imputation similar to that of the primary endpoint analysis. In addition, descriptive statistics involving the sample size, the number of responders, and proportion of responders will be summarized by treatment group. Details regarding the methods of estimation to be performed at Weeks 32 and 52 will be provided in the SAP.

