8.2. Baseline Disease Characteristics

Baseline clinical characteristics will be summarized descriptively by treatment arm, which will include the following:

- Duration of plaque psoriasis (from date of diagnosis to the date of informed consent; year, presented one digit after the decimal point)
- Duration of plaque psoriasis categories (< 10, 10 to < 20, \geq 20 years)
- The primary manifestations for stratifications: scalp psoriasis, nail psoriasis, palmoplantar psoriasis, genital psoriasis, and psoriasis in visible locations
- Baseline DLQI total score
- Baseline DLQI score categories (>10 to 20, >20)

Apremilast**Statistical Analysis Plan. Protocol CC-10004-PSOR-020****Amgen INC.**

- Baseline sPGA score of visible locations: 0 (clear), 1 (almost clear), 2 (mild), 3 (Moderate), 4 (Severe)
- Baseline ScPGA score: 0 (clear), 1 (almost clear), 2 (mild), 3 (Moderate), 4 (Severe)
- Number of affected nails: 0, 1, ≥ 2
- Baseline NAPSI score for the target nail
- Baseline sPGA-G score: 0 (clear), 1 (almost clear), 2 (mild), 3 (Moderate), 4 (Severe)
- Baseline PPPGA score: 0 (clear), 1 (almost clear), 2 (mild), 3 (Moderate), 4 (Severe)
- Baseline pruritus NRS score
- Baseline skin discomfort/Pain VAS score
- Baseline PASI score
- Baseline PASI score categories (3 to 5, >5 to 10)
- Baseline BSA (%)
- Baseline BSA (%) category (≤ 3 , >3 to 5, >5 to 10, >10)
- Baseline EQ-5D vas and EQ-5D index value
- Baseline WPAI: PSO: percentage of work missed due to Psoriasis and overall work impairment for those who were currently employed; percentage of work impairment and percentage of daily activity impairment due to Psoriasis among all subjects
- Baseline PNQ: the importance of each of the 25 treatment goals will be summarized with count (%) by missing, does not apply to me, not at all, somewhat, moderately, quite and very.

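### PASI <3 at Week 16 is tested without adjusting for baseline PASI, although entry PASI of 3 to 10 largely sets how hard the target is to reach, so the test gives up power

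*SAP*

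**What the plan says.** SAP 9.4.1, Table 5, gives the endpoint as "Proportion of subjects who achieve Psoriasis Area Severity Index (PASI) < 3 at Week 16" and its main analysis as "CMH test adjusting for the stratification factor on data with MI". The supportive analysis is "CMH test adjusting for the stratification factor on data with LOCF and data with NRI", so the adjustment is the same throughout. Protocol 9.6.2 agrees: "For discrete endpoints, the CMH estimation method stratified by the randomization strata" is the method. The only stratification factor is the five-level manifestation type (SAP 4.3).

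Eligibility (Protocol 4.2) reads "Subject has a PASI score ranging from ≥ 3 to ≤ 10 at baseline".

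Baseline PASI is used in two places, and neither is a treatment comparison:
- the imputation model: "The missing values at each visit will be imputed based on treatment, stratification factor, and the score of interest at baseline and previous visits" (SAP 9.4.1);
- the baseline table, which also bands it as 3 to 5 and above 5 to 10 (SAP 8.2).

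The continuous endpoints are handled differently. The DLQI row of Table 5, for example, is "ANCOVA model adjusted by baseline DLQI score, treatment, stratification factor on data with MI", and every other ANCOVA row also carries its own baseline score.

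**The concern.** The responder cut-off lies exactly at the lower entry limit, so subjects start at very different distances from it. Among the binary endpoints in the SAP 9.2 sequence, this one alone puts an absolute threshold on a score that has a baseline value. DLQI response is a change score, and a 4-point fall is possible for everyone because entry requires DLQI above 10. PBI has no baseline score of its own.

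If baseline PASI predicts response, a test that ignores it leaves explainable variation in the error term. Randomisation balances baseline PASI on average, but it neither recovers that precision nor corrects a chance imbalance in the trial at hand.

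More than one endpoint is at stake. Under SAP 9.2, PASI <3 comes sixth, and PBI, EQ-5D and WPAI can be claimed only if it succeeds. The sample size was set on DLQI response (SAP 4.4), and no power is stated for PASI <3.

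**Working it through.** **1. The plan's own figure.** The only stated power is for DLQI response: 0.70 against 0.50, 140:70, two-sided 0.05 (SAP 4.4).
- Standard error under the alternative: √(0.50×0.50/70 + 0.70×0.30/140) = 0.0712. Unpooled power: Φ(0.20/0.0712 − 1.96) = 0.802.
- With the pooled null variance (mean rate 133/210 = 0.633, standard error 0.0705): Φ((0.20 − 1.96×0.0705)/0.0712) = 0.807, as stated.
- At 255 subjects (170:85) the unpooled formula gives 0.872, as stated in Protocol 9.3.

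These figures say nothing about PASI <3.

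**2. How far each subject must move.** To get below 3 from baseline b, the proportional fall must exceed 1 − 3/b.

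| Entry PASI | Fall needed |
|---|---|
| 3.0 | above 0% (0.1 point on a one-decimal score) |
| 5 | above 40% |
| 7 | above 57% |
| 10 | above 70% |

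**3. Chance imbalance.** Assume 276 subjects split 184:92 and entry PASI uniform on 3 to 10, so SD = 7/√12 = 2.02. The standard error of the difference in mean baseline PASI is 2.02×√(1/184 + 1/92) = 0.258. About one trial in 20 would therefore show a difference beyond 1.96×0.258 = 0.5 points.

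**4. Simulated power, multiplicative model.** Documented inputs: 2:1 allocation in permuted blocks within five strata, PASI 3 to 10, two-sided 0.05, N = 210 or 276. Assumed inputs:
- stratum shares of 35, 15, 10, 10 and 30%;
- baseline PASI uniform, or normal (6.5, SD 2) truncated to 3–10;
- Week 16 PASI = baseline × a lognormal factor, with log SD 0.5, 0.8 or 1.2;
- placebo and apremilast rates of 0.20/0.35, 0.20/0.40 or 0.30/0.45;
- no missing data.

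This makes 36 scenarios of 1,500 trials each. All methods were applied to the same simulated trials. Gains are in power points over the planned five-stratum CMH, with 12 scenarios per row.

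| Log SD | Correlation of baseline with response | Gain, logistic with continuous baseline PASI | Gain, CMH strata also split at PASI 5 |
|---|---|---|---|
| 0.5 | −0.36 to −0.46 | 3.6 to 12.2 | 1.8 to 7.3 |
| 0.8 | −0.24 to −0.30 | 1.4 to 5.2 | −0.2 to 2.7 |
| 1.2 | −0.16 to −0.21 | 0.2 to 3.8 | −0.8 to 1.5 |

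The logistic gain is below 2 points in 9 scenarios, 2 to 7 in 20 and above 7 in 7. Examples with uniform baseline:
- N = 276, 0.20 vs 0.35: 0.750 to 0.839 (log SD 0.5) and 0.758 to 0.807 (log SD 0.8);
- N = 210, 0.30 vs 0.45, log SD 0.5: 0.582 to 0.704.

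Under the null (6,000 trials, two settings) the planned CMH rejected 4.6% and 4.7%, and the logistic model 4.3% and 4.6%.

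**5. Simulated power, additive model.** Here Week 16 PASI is linear in baseline, with assumed slope 0.4 to 0.9.
- N = 255, residual SD 2.5: for slopes 0.9, 0.6 and 0.4, adjustment was worth 17.4%, 8.2% and 3.8% more subjects. The variance reduction is 1 − 1/1.174 = 15% at the top and 1 − 1/1.038 = 4% at the bottom. Power rose from 0.913 to 0.949, 0.955 to 0.970 and 0.949 to 0.961.
- N = 210 and 276, residual SD 2.5 to 3.5, rates about 0.22–0.30 vs 0.39–0.43, using the standardised risk difference proposed below: variance fell by about 5% to 23% and power rose by about 2 to 11 points. Null rejection was 4.4% to 6.2%, against 4.5% to 5.9% for the planned CMH.

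**The case against.** The strongest reply is that nothing here is an error. Stratifying by the randomisation factor is the protocol's stated method, the SAP applies it consistently to all binary endpoints, and its type I error holds. That stands: the point is about efficiency only.

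The size is not anchored in the documents, which give no PASI <3 rates, no baseline PASI distribution and no Week 16 variability. That also stands. With wide variability (log SD 1.2) the gain is 0.2 to 3.8 points. Where the planned test already exceeds 90% power (0.20 vs 0.40 at N = 276), it is 0.2 to 3.8 points as well. The 255-subject simulation also uses the protocol's total rather than the SAP's 276; the runs at 210 and 276 address this and show gains at least as large at the upper end.

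Only three listed endpoints follow PASI <3, and SAP 5.1 still calls non-primary p-values summary statistics. But SAP 9.2 sets the hierarchy and SAP 13 declares it as a deliberate departure from the protocol, so the gate is real.

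Finally, replacing the CMH needs a variance method and a rule for small strata. This is fair and is covered in the fix. It is no reason to leave the baseline value out, since the plan adjusts every ANCOVA endpoint for its own baseline.

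**Conclusion.** The concern holds. The main test of PASI <3 ignores a baseline value that fixes the required reduction anywhere from just above 0% to above 70%. The test is unbiased and valid but less powerful than it could be. Adjustment never lowered power in the 36 multiplicative scenarios, and it raised power in the additive runs. A gain of 1 to 4 points, as in the 255-subject runs, is at the conservative end; about 12 points is the most seen.

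The required reduction is arithmetic. How strongly baseline PASI predicts response is not documented, and that decides where in the range the loss falls: clear if Week 16 PASI tracks baseline closely, small if it varies widely. Because the test gates three further endpoints and the remedy costs little, the change should be made.

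**What to change.** Keep the endpoint and its place in the sequence, and change its main analysis:

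1. In each of the 25 imputed data sets, fit a logistic model with treatment, manifestation stratum and continuous baseline PASI.
2. Predict every subject's response probability under each arm, average by arm and take the difference (the standardised risk difference). Name its standard error in the SAP, for example delta-method or robust.
3. Combine the 25 estimates with MIANALYZE, as already planned for the other results.
4. Pre-specify a fallback for sparse strata, such as pooling small ones. Stratum sizes may be uneven, since the requirement for equal block-randomisation across manifestations was removed.
5. Keep the planned CMH as supportive, beside the LOCF and NRI analyses.

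Adding the two PASI bands to the CMH strata is simpler but recovers less, and it doubles the strata to ten. Reporting the adjusted analysis only as supportive would sharpen the estimate but would not help the gated test.

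The cost is a revised row in Table 5, a short text change in SAP 9.4.1, an entry in SAP 13 for the departure from Protocol 9.6.2, and minor code. No new data are needed, because baseline PASI is required for eligibility. The change must be fixed before the Week 16 data transfer, by which time SAP section 2 says the plan will be signed.

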4.2.5.6. Psoriasis Area and Severity Index (PASI)

The PASI is a measure of psoriatic disease severity taking into account qualitative lesion characteristics (erythema, thickness, and scaling) and degree of skin surface area involvement on defined anatomical regions. The PASI is a validated instrument that has become standard in clinical trials for psoriasis.

Psoriasis Area Severity Index scores range from 0 to 72, with higher scores reflecting greater disease severity. Erythema, thickness, and scaling are scored on a scale of 0 (none) to 4 (very severe) on 4 anatomic regions of the body: head, trunk, upper limbs, and lower limbs. Degree of involvement on each of the 4 anatomic regions is scored on a scale of 0 (no involvement) to 6 (90% to 100% involvement). The total qualitative score (sum of erythema, thickness, and scaling scores) is multiplied by the degree of involvement for each anatomic region and then multiplied by a constant. These values for each anatomic region are summed to yield the PASI score. The PASI score will be set to missing if any severity score or degree of involvement is missing. PASI scores will be presented with one digit after the decimal point.

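### SAP 9.4.1 rounds MCMC-imputed PASI and PBI to whole numbers, which moves the PASI <3 and PBI ≥1 cut-offs for intermittently missing Week 2 and Week 4 values (PBI: Week 4 only)

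*SAP*

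**What the plan says.** SAP 9.4.1 covers the secondary scores together: "For each continuous-like efficacy assessments, the SAS procedure MI will be used to impute missing values for each scheduled visit". EQ-5D and WPAI: PSO are excepted. The visits in the imputation are "Baseline (Week 0), and Weeks 2 (if applicable), 4, and 16".

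There are two steps.

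- **MCMC.** Its purpose is "to create M=25 imputed data sets with monotone missing patterns". The minimum and maximum are set to suit each score, but the rounding is not: "the imputed values will be rounded to integers and a single chain will be used to produce imputations". The SAP adds: "This step will be skipped if the data missing pattern is monotone".
- **Predictive mean matching.** After that, "the predictive mean matching method will be used to impute the remaining missing values for the 25 data sets with monotone missing patterns". No rounding is stated for this step.

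Response is derived from the imputed score after both steps. The binary analyses are not confined to Week 16: "Same analyses will also be conducted for other scheduled assessment visits (e.g., at Week 2 and Week 4) during the Placebo-controlled Phase".

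On the scores themselves, SAP 4.2.5.6 says "PASI scores will be presented with one digit after the decimal point", and the worksheet in protocol Appendix J also rounds to one decimal. SAP 4.2.5.5 defines PBI as an importance-weighted mean of item scores, and protocol 6.4.11 gives its range as 0 to 4. SAP 9.3 words the rounding rule for DLQI in the same way. There it fits, because DLQI is a sum of integer items.

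**The concern.** A rounding unit of 1 is coarse for scores judged against PASI <3 and PBI ≥1. Both cut-offs are whole numbers, so rounding to the nearest integer pulls values just below the cut-off up onto it. For PASI this turns a responder into a non-responder. For PBI it turns a non-responder into a responder. The error always goes the same way for a given score, so averaging over 25 imputations does not remove it.

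At stake are the multiple-imputation responder analyses at Weeks 2 and 4. The identical wording in SAP 9.3 suggests that the rule was taken from DLQI without adapting it, but the documents do not say so.

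**Working it through.** The documents give no figure for this point, so there is none to reproduce.

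**1. Which values change status.** Applying round-to-nearest-integer to the PASI grid (steps of 0.1) and a PBI grid (steps of 0.01):

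| Score | Cut-off in SAP 4.2.2 | Values that change status | Working cut-off |
|---|---|---|---|
| PASI | <3 | 2.5, 2.6, 2.7, 2.8, 2.9 become 3 | <2.5 |
| PBI | ≥1 | 0.50 to 0.99 become 1 | ≥0.5 |

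**2. Which cells are exposed.** MCMC fills only what is needed to make the pattern monotone, that is, a missing visit followed by an observed one.

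- PASI is scheduled at Baseline and Weeks 2, 4 and 16 (protocol Table 3), so the exposed responder results are Weeks 2 and 4.
- In this phase the PBQ is scheduled at Weeks 4 and 16 only, so the exposed PBI cell is a missing Week 4 value with Week 16 present.
- Week 16 comes last, so a missing Week 16 value is never an intermittent gap. It goes to predictive mean matching, which draws from observed Week 16 values.
- Rounding can still reach later results indirectly. Filled earlier scores serve as predictors, and filled Week 2 or Week 4 values can be drawn as donors at the same visit.

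**3. Share of MCMC-filled values that change status.** The normal shape, means and SDs are assumptions.

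PASI, SD 2: P(2.5 ≤ X < 3) = Φ((3 − m)/2) − Φ((2.5 − m)/2)

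- m = 5: Φ(−1.00) − Φ(−1.25) = 0.053
- m = 4: Φ(−0.50) − Φ(−0.75) = 0.082
- m = 3.5: Φ(−0.25) − Φ(−0.50) = 0.093

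Compared with rounding to 0.1 rather than no rounding, the PASI range is slightly lower, 4.7% to 8.3%.

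PBI, SD 1: P(0.5 ≤ X < 1) = Φ(1 − m) − Φ(0.5 − m)

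- m = 1: Φ(0) − Φ(−0.5) = 0.191
- m = 1.5: Φ(−0.5) − Φ(−1.0) = 0.150
- m = 2: Φ(−1.0) − Φ(−1.5) = 0.092

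**4. Effect on the Week 4 response rate.** Shift = share changed × fraction intermittently missing. That fraction is assumed to be 2% to 10%.

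- PBI: 0.092 × 2% = 0.2 points up, to 0.191 × 10% = 1.9 points up.
- PASI: 0.053 × 2% = 0.1 points down, to 0.093 × 10% = 0.9 points down.

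**5. Effect on the treatment difference.** Assume equal intermittent missingness in both arms, and place the arms at opposite ends of the assumed means.

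- PBI: (0.191 − 0.092) × 10% = 1.0 point; at 2% missing, 0.2 points.
- PASI: (0.093 − 0.053) × 10% = 0.4 points.

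**6. Simulation of both steps for PASI.** Assumptions: N = 276 at 2:1, assumed PASI means and SDs, correlation 0.65, 24% dropout by Week 16, 5% random extra missingness at each of Weeks 2 and 4, MCMC by arm only, K = 5, 10 imputations, 40 trials.

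| PASI <3 | Integer rounding | No rounding |
|---|---|---|
| Week 4, MCMC-filled cells (true rate 29.8%) | 23.4% | 30.3% |
| Week 4, all subjects | 28.7% | 29.0% |
| Week 16, all subjects | 41.3% | 41.2% |
| Week 16, treatment difference | 18.5 points | 18.5 points |

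No Week 16 cell was filled by MCMC, and every imputed Week 16 value was an observed donor value.

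**The case against.** The strongest reply is that nothing tested depends on this. PASI <3 and PBI ≥1 are named endpoints at Weeks 16, 32 and 52 only (SAP 4.2.2), and the hierarchy in SAP 9.2 contains only Week 16. Weeks 32 and 52 use non-responder imputation, not this procedure (SAP 9.4.2). The MCMC step is skipped if the pattern is already monotone. The wide visit windows in SAP Table 2, where Days 22 to 70 count as Week 4, make intermittent gaps less likely. The early-visit binary analyses are repeated with LOCF and non-responder imputation, which do not use the rounding. The upper figure of 1.9 points combines the largest share with the largest assumed missingness, and a rule common to both arms moves the difference less than the rate.

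All of that stands, and it limits the size. It does not make the rule right: it conflicts with the scales of two scores and gives wrong responder status in analyses that the SAP plans.

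Three stronger readings are tempting, and the documents do not support them:

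- **Week 16 responder results are shifted.** That would require MCMC to fill every missing cell. The SAP uses it only to reach a monotone pattern.
- **PBI is affected at Week 2.** No PBQ is scheduled then.
- **BSA percent change is distorted.** The recorded precision of BSA is not given. It is estimated in handprints of about 1% each, and if it is recorded in whole percents, integer rounding is right. It also has no responder cut-off. If BSA were recorded more finely, a missing baseline BSA would be filled, rounded and used as the percent-change denominator. BSA is not scheduled at screening, so this could happen, but it is probably rare.

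**Conclusion.** Wrong as written; minor. For intermittently missing values filled by MCMC, the working cut-offs become PASI <2.5 (Weeks 2 and 4) and PBI ≥0.5 (Week 4). This understates PASI response and overstates PBI response in the planned early-visit analyses. The cut-off shift follows from the SAP text by arithmetic.

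The sizes rest on assumptions that the documents do not supply: the score distributions, and 2% to 10% intermittent missingness. Under these, the Week 4 PBI rate rises by at most about 1.9 points. The between-arm effect is at most about 1 point, provided that intermittent missingness is similar in the two arms. The simulated Week 4 PASI rate moved by 0.3 points overall. The tested Week 16 endpoints are essentially unaffected, given the reading that MCMC fills intermittent gaps only.

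**What to change.** In SAP 9.4.1, set the MCMC rounding per score, as is already done for the minimum and maximum:

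- PASI: 0.1
- PBI: no rounding, or 0.01
- BSA: the recorded precision (an integer if it is recorded in whole percents), stated in the SAP
- DLQI, itch NRS and skin discomfort/pain VAS: integers, as now

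Leave the predictive mean matching step as written.

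The cost is one rounding option per variable in the PROC MI call and one sentence in the SAP. No endpoint, test or sample size changes.
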